Any adverse experience that meets reporting guidelines for SAEs must be reported to the CRA for the study in the CCTO within 24 hours of knowledge of the event. The CRA will follow AE reporting plans per institutional policies and applicable regulations. All qualified AEs will be reported to the Investigators, U. S. Army Medical Research and Material Command Human Subjects Research Review Board (HSRRB), FDA, IRB, Medical Monitor, and the UAMS Research Support Center according to this plan.

All AEs and SAEs must be recorded in the appropriate section of the CRF. The report should include, whenever possible, the investigator's written medical judgment as to the relationship of the AE/SAE to study medications(s) (i.e., "probable", "possible" or "unrelated").

Unanticipated problems involving risk to subjects or others, serious adverse events related to participation in the study and all subject deaths should be promptly reported by [contact]), by email ([contact]), or by [contact]) to the U.S. Army Medical Research and Materiel Command, Human Subjects Research Review Board (HSRRB). A complete written report should follow the initial notification. In addition to the methods above, the complete report can be sent to the U.S. Army Medical Research and Materiel Command, ATTN: MCMR-ZB-QH, [name].

17. Monitoring

- a. **Medical Monitor:** The Medical Monitor, Principal Investigator and study staff will meet to review safety data after each cohort has been enrolled and prior to enrollment of the next cohort. Any death will trigger an additional urgent meeting.
- b. **Data Monitor:** UAMS is the IND Sponsor. One (or more) Data Monitor(s) will be appointed by the monitoring division of the UAMS Research Support Center (RSC) to assure that the rights and well-being of human subjects are protected, that the data are accurate, complete and verifiable from source documents and that the trial is conducted in compliance with

currently approved protocol/amendments, with GCP, and with the applicable regulatory requirements set forth in 21 CFR 312.

The Data Monitor(s) will be familiar with the investigational products, the protocol, the informed consent form, any other information provided to the subjects, SOPs, GCP and applicable regulatory requirements.

Data Monitor(s) will have access to research subjects' medical records and other study-related records. The investigator agrees to cooperate with the study coordinator and Medical Monitor to ensure that any problems detected in the course of these monitoring visits are resolved. Personal contact between the Data Monitor, Medical Monitor, study staff and the investigator will be maintained throughout the clinical trial to assure that the investigator is fulfilling his/her obligations and that the facilities used in the clinical trial remain acceptable.

- 1) Pre-investigation Site Visit:** A pre-investigation site visit will be performed by the Data Monitor in order to inspect the facility where the study is going to be conducted, and to assure that the investigator and his/her staff understand the protocol and agree to comply with the current regulations for clinical trial conduct in human subjects (21 CFR 312, 21 CFR 50, 21 CFR 56, 21 CFR 11, 21 CFR 21). The Data Monitor will document the IRB approval and generate a special report that will allow subject enrollment on the trial to begin.
- 2) Periodic Site Visits:** The first visit of the Data Monitor will occur as soon as possible after the first research subject has enrolled in the study. Subsequent monitoring visits will take place approximately quarterly based on enrollment. The Data Monitor will review the CRFs, source data/documents and other trial-related records for accuracy, consistency and completeness. Enrollment of research subjects after meeting eligibility criteria and signing a consent form will be documented. Missing visits, withdrawals and subject recruitment rate will be monitored.
- 3) Investigational Products:** The Data Monitor will verify that the storage conditions are appropriate and that the investigational drug is being dispensed to eligible subjects according to the study protocol. The Data Monitor will verify that there are accurate records of the receipt, use and return of the investigational product.
- 4) Monitoring Report:** After each monitoring visit a separate monitoring report will be generated and submitted to the investigator, U. S. Army Medical Research and Material Command Human Subjects Research Review Board, research staff and the Medical Monitor. This report will include significant findings related to deficiencies and deviations from the protocol, SOPs, GCP and the applicable regulatory requirements and actions taken to prevent recurrence of the detected deviations. The report will make recommendations for actions to be taken to secure compliance. The study team, which includes the PI, subinvestigators, biostatistician, Medical Monitor and the study coordinator, will meet after each cohort completes the protocol to review AEs and review monitoring reports in order to make adjustments necessary to protect the research subjects and the integrity of the trial.
- 5) Research Subject Safety and Stopping Rules:** If 3 SAEs occur with attribution to the study drug, the trial will be suspended until further review is completed by the

Medical Monitor, PI, sponsor and FDA. This will be accomplished by the study team, the PI, Co-PI, biostatistician, Medical Monitor and CRA, either at the regular meeting or a special meeting called by the Medical Monitor or the PI because of the SAEs. The study will be stopped upon Death not related to cancer or two Grade 4 Toxicities related to the study article.

6) Audits: An audit by UAMS will be scheduled after the completion of the first cohort. The audit will follow UAMS' standard auditing procedure.

18. Bibliography

1. Sabbatini, P. J., Kudryashov, V., Ragupathi, G., Danishefsky, S. J., Livingston, P. O., Bornmann, W., Spassova, M., Zatorski, A., Spriggs, D., Aghajanian, C., Soignet, S., Peyton, M., O'Flaherty, C., Curtin, J., and Lloyd, K. O. Immunization of ovarian cancer patients with a synthetic Lewis(y)-protein conjugate vaccine: a phase 1 trial. *Int J Cancer*, 87: 79-85., 2000.
3. Vollmers, H. P. and Brandlein, S. The "early birds": natural IgM antibodies and immune surveillance. *Histol Histopathol*, 20: 927-937., 2005.

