Dose Justification: Immunologic testing in mice indicates that there is no difference in antibody responses to P10s in mice between the 300 µg and 500 µg dose (GLP Report: “Determination of the Safety and Tolerability of Immunization with LeY Peptide Mimotope Vaccine in Mice”). Dose escalation is meant to test the safety of the preparation in terms of its non-immunological toxicity. In this case the assumption is that the putative adverse effects increase monotonically with the dose, and exploring the higher-than-necessary doses ensures safety of the lower ones. As for the immunological effects, they are characteristically non-monotonic with an optimal effect in a specific dose range, and weaker effects and even induction of tolerance for doses much higher or lower than the optimal one. Thus, the classical dose escalation trial may or may not detect the immunological effects, including adverse autoimmune phenomena. A dose-escalation algorithm better suited for determining the immunological impact should include both increasing and decreasing arms, and should be terminated when doses beyond the one that leads to optimal immunological effect are reached, provided they are tolerated otherwise. When increasing immunological effect is detected in one of the arms, the other one may be discontinued, if not necessary for the toxicology study.

4. Trial Objectives

a. Primary Objective – Safety: The safety and tolerability of the P10s-PADRE/ MONTANIDE™ ISA 51 VG vaccine will be determined by toxicity assessments throughout the duration of the study. Subjects will be evaluated for toxicity using the National Cancer Institute (NCI) Common Terminology Criteria for Adverse Events (CTCAE) Version 4.0. A toxicity of Grade 3 or higher will be considered a dose limiting toxicity (DLT).

b. Secondary Objectives – Immune Response:

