- f. **Dose Limiting Criteria:** Subjects who develop any grade 3 or greater toxicity as per NCI CTCAE v. 4 toxicity criteria, Grade 2 or greater autoimmune toxicity with the exception of vitiligo, or Grade 2 or greater hypersensitivity reactions will be treated and referred for additional care as indicated with systemic steroids, topical steroids, epinephrine or Benadryl. These subjects will be removed from the study and will be followed as per protocol defined monitoring and/or until resolution of toxicity.
- g. **Dose Assignment:** Subjects will be treated with vaccine admixed with MONTANIDE™ ISA 51 VG on weeks 1, 2, 3, 7 and 19 in cohorts according to the following dosing diagram:

DLT and the immune-response endpoints are defined in Section 4, “Trial Objectives”. Upon evaluation of all subjects in a cohort (3 or 6 per dose level), the decision whether to escalate, de-escalate or stop will proceed according to the cohort-appropriate schedule shown in **Tables 1, 2, and 3**.

Table 1: Toxicity Decision Rules for Initial Cohort (300 µg Vaccine Dose)

DLTs/ Cohort¹	Action
0/3	Begin accrual to Escalation Cohort
1/3	Expand Initial Cohort to 6 subjects
1/6	Begin accrual to Escalation Cohort
2/6, 3/6, or 4/6	Begin Accrual to De-Escalation Cohort
2/3 or 3/3	Begin Accrual to De-Escalation Cohort

¹ DLT = Dose-Limiting Toxicity

Table 2: Toxicity Decision Rules for Escalation Cohort (500 µg Vaccine Dose)

DLTs/ Cohort¹	Action
0/3 or 1/3	Expand cohort to 6 subjects
1/6	Stop: Declare escalation dose to be MTD ²
2/6, 3/6, or 4/6	Stop: Previous dose level is MTD ²
2/3 or 3/3	Stop: Previous dose level is MTD ²

¹ DLT = Dose-Limiting Toxicity² MTD = Maximum Tolerated Dose**Table 3: Toxicity Decision Rules for De-Escalation Cohort (100 µg Vaccine Dose)**

DLTs/ Cohort¹	Action
0/3 or 1/3	Expand cohort to 6 subjects.
1/6	Stop: De-escalation dose level is the MTD ²
2/6, 3/6, or 4/6	Stop: De-escalation dose level is above MTD ²
2/3 or 3/3	Stop: De-escalation dose level is above MTD ²

¹ DLT = Dose-Limiting Toxicity² MTD = Maximum Tolerated Dose

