Subjects will receive up to 5 planned vaccine doses unless they withdraw from the study or develop a dose limiting event as stated above, at which time they will discontinue the injections and be removed from the study. There will be no dose modifications for toxicity. Special attention will be given to toxicities mediated by autoimmune mechanisms, such as colitis, thyroiditis or systemic lupus erythematosus (SLE), as well as to injection-site local reactions or allergic reactions. The NCI CTCAE Version 4.0 will be used for toxicity and SAE reporting. A copy of the CTCAE Version 4.0 can be downloaded from the Cancer Therapy Evaluation Program (CTEP) home page or viewed in **APPENDIX A**. All appropriate treatment areas have access to a copy of the CTCAE Version 4.0.

Any subject may voluntarily revoke consent and withdraw from the study at any time. A subject may be terminated early for the following conditions: (i) non-compliance, (ii) an unrelated intercurrent illness that may affect assessment or place the subject at risk for AEs or require systemic steroids, (iii) deterioration in performance status so as to make participation a hardship for the subject, (iv) for toxicity as determined by the DLT criteria, or (v) for any reason that the investigator feels it is not in the subject's best interest to continue.

- b. Benefits:** As this is the first time Mimotope P10s-PADRE will be administered to humans, there are no clearly defined benefits to subjects of this study. However, this vaccine may potentiate an immune response which could improve median progression-free survival and overall survival of cancer patients.
- c. Injury:** For DOD-funded research, participants can receive medical care at an Army hospital or clinic free of charge. If participants pay out-of-pocket for medical care elsewhere for injuries caused by this research study, they should contact the Principal Investigator. If the issue cannot be resolved, contact the U.S. Army Medical Research and Materiel Command (USAMRMC) Office of the Staff Judge Advocate (legal office) at [contact]/[name]

9. Specimen Handling

Samples will be stored in the UAMS Tissue Procurement Facility, located in room B.018 of the hospital. Cryotubes that contain specimens will be labeled with barcodes. The coded number is linked to patient identification and time of blood draw. Specimens will be stored frozen at -80°C

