⁵The DTH skin test at prestudy will test the subjects' immunocompetency. Control antigens, Trichophyton Antigen and Candida antigen, will be administered id and the resulting induration will be ready at 48 - 72 hours post injection.

⁶ The DTH skin tests on weeks 5, 9 and 21 will test the DTH response to Mimotope P10s-PADRE. Trichophyton Antigen and Candida antigen will be administered id alongside Mimotope P10s-PADRE as control antigens to assess immunocompetency. DTH skin test indurations will be read at 48 – 72 hours post injection.

⁷ Visits must occur at set time points mentioned in the study calendar (+/- 3 days) with the exception of reading the skin test which must occur 48-72 hours post administration.

⁸ Concomitant medications will be collected from registration to end of treatment.

⁹ Post vaccine administration, the following vital signs will be monitored every 15 minutes (+/- 5 minutes) for one hour: blood pressure, temperature, and pulse.

¹⁰ Follow up visits shall begin with the next scheduled standard of care appointment and then shall occur every six months for five years and then yearly until death.

11. Criteria for Evaluation

Primary Objective – Safety:

- **Determination of DLT:** See Section 8, “Risks and Toxicities to be Monitored”. Any event that meets the dose limiting criteria will be determined a dose limiting toxicity.

Secondary Objectives – Immune Response:

- **Immunological Evaluation:** Serum will be collected at the Study Lab time points indicated in the study calendar in Section 10. Samples will be collected and stored by the UAMS Cancer Institute Tissue Bank following established Tissue Bank SOPs. IgM and IgG titers to TACAs will be evaluated by ELISA on TACA adhered to plates and FACS analysis of TACA adhered to liposomes. A positive TACA-directed immune response will be defined as an anti-TACA serum antibody titer of 1:40 for a baseline pre-vaccination titer of 0 or a \geq 4-fold increase over baseline titer > 0 (1, 11). Subjects will be judged to have had an adequate immune response if they have a positive TACA-directed immune response at any one of the first five designated time points following vaccine administration (Weeks 2, 3, 4, 7 and 9). The value of a booster immunization will be determined by anti-TACA IgM and IgG titers obtained from study labs collected on week 21.

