It should be noted that the primary objective of this study is to ensure the safety of the mimotope vaccine. Because of sample size, these studies only provide a qualitative assessment of vaccine immunogenicity. However, our immunization schedule should favor the generation of antibodies (1, 11, 42). A positive TACA-directed immune response will be defined as an anti-TACA serum antibody titer of 1:40 for a baseline pre-vaccination titer of 0 or a \geq 4-fold increase for a baseline titer > 0 (1, 11). A subject will be judged to have had an adequate immune response if they have a positive TACA-directed immune response at any one of the first five indicated time points following vaccine administration on the study calendar (Section 10, Study Lab Weeks 2, 3, 4, 7 and 9). An additional immune-response endpoint will be the DTH response to Mimotope P10s-PADRE. The components of the DTH response, namely, the induration in mm across two diameters, will be tabulated by antigen (the mimotope vs. the two DTH controls) for each subject at the indicated time points on the study calendar. An induration of >5 mm in at least one diameter will be considered a positive DTH response.

b. Data Analysis Plan: Toxicity will be graded according to the NCI CTCAE Version 4.0. All toxicities observed in a study subject will be enumerated and reported in terms of type (organ affected or laboratory determination such as absolute neutrophil count), severity (by NCI Common Toxicity Criteria (CTC) and nadir or maximum values for the laboratory measures), time of onset (i.e. dose number), duration and reversibility or outcome. A toxicity meeting the dose limiting criteria as stated above will be scored as a DLT. The number and proportion of subjects in each dose cohort who suffer a DLT will be reported. The number of DLTs observed will be reported by dose cohort, both overall and also broken down by CTCAE category.

To meet the secondary objective of determining the humoral response against TACAs, the anti-TACA serum titers measured from subjects' blood samples will be collected at pre-study and on weeks 2, 3, 4, 7, and 9. IgM and IgG titers to TACAs will be evaluated by ELISA and

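### The dose-decision tables and the safety analysis use different DLT definitions, so a Grade 2 autoimmune or hypersensitivity event can change the next dose and the declared MTD

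*Combined protocol and SAP*

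**What the plan says.** - **Section 4.a (primary objective):** "A toxicity of Grade 3 or higher will be considered a dose limiting toxicity (DLT". This is the only DLT criterion in Section 4.
- **Section 7.g, directly above Tables 1-3:** "DLT and the immune-response endpoints are defined in Section 4". The tables that set the dose are therefore tied to the Grade 3 rule.
- **Section 7.f, headed Dose Limiting Criteria:** besides Grade 3 or higher toxicity it lists "Grade 2 or greater autoimmune toxicity with the exception of vitiligo, or Grade 2 or greater hypersensitivity reactions". These subjects are treated, removed from study and followed. Section 7.f itself does not use the term DLT.
- **Section 11 (determination of DLT):** "Any event that meets the dose limiting criteria will be determined a dose limiting toxicity". It cites Section 8 for the criteria. Section 8 lists none and only points back to a dose limiting event already described.
- **Section 8 (early termination):** one ground is removal "for toxicity as determined by the DLT criteria".
- **Section 12.b:** "A toxicity meeting the dose limiting criteria as stated above will be scored as a DLT". It does not name the section meant.
- **Sections 7.g and 12.a:** subjects who withdraw without a DLT are replaced; those who withdraw with one are evaluable for the MTD.

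**The concern.** The DLT count is the primary safety result, and under Section 12.a it alone decides whether to escalate, expand, de-escalate or stop. The rule that drives those decisions and the rule that will be used to report them do not classify the same events as DLTs.

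The events in dispute matter for this product. The trial is first-in-human, hypersensitivity up to anaphylaxis is a listed risk, and Section 8 says "Special attention will be given to toxicities mediated by autoimmune mechanisms" and also names allergic reactions. Under the definition that Tables 1-3 cite, a Grade 2 event of this kind is serious enough to take the subject off study, yet it does not count against the dose. Later subjects could then receive a higher dose, and the final report could show DLTs that the escalation decisions had left out.

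**Working it through.** **The plan's own figure.** Section 12.a says nine subjects are needed if no DLT occurs. Table 1 at 0/3 uses 3 subjects and escalates; Table 2 at 0/3 expands to 6. 3 + 6 = 9, as stated. This holds under either definition, so the figure does not show which one was meant.

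**Same events, different table row.** These cases need no assumed rate. They count the subjects as enrolled, without replacement.

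| Dose | Events (different subjects) | Under 4.a | Under 7.f |
|---|---|---|---|
| 300 µg | one Grade 2 hypersensitivity in 3 | 0/3: escalate | 1/3: expand to 6 |
| 300 µg | two such events in 3 | 0/3: escalate | 2/3: de-escalate |
| 300 µg | one Grade 3 and one Grade 2 immune in 6 | 1/6: escalate | 2/6: de-escalate |
| 500 µg | one Grade 3 and one Grade 2 immune in 6 | 1/6: MTD is 500 µg | 2/6: MTD is the previous dose |

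If removal under 7.f counts as withdrawal, 4.a would require a removed subject to be replaced. The 4.a column then holds provided the replacements have no DLT. Not every event changes the action: in Tables 2 and 3, 0/3 and 1/3 both lead to expansion.

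**How often.** The documents give no event rates. Assumptions:
- 10% of subjects have a Grade 3 or higher event.
- Independently, a proportion g has a Grade 2 immune event, with g = 2%, 5%, 10% or 20%.
- Rates are the same at both doses.
- 0/6 in Table 2, which has no such row, is read as a pass like 1/6.

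Per-subject DLT probability p:
- 4.a: p = 0.10
- 7.f: p = 1 − 0.9(1 − g) = 0.118, 0.145, 0.19, 0.28
- 4.a with removed subjects replaced: p = 0.10/(1 − 0.9g) = 0.102, 0.105, 0.110, 0.122

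Formulas:
- Table 1: P(escalate) = (1 − p)³ + 3p(1 − p)⁵
- Table 2: P(pass at 500 µg) = (1 − p)⁶ + 6p(1 − p)⁵
- P(500 µg declared MTD) = P(escalate) × P(pass)

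Under 4.a: P(escalate) = 0.729 + 0.177 = 0.906; P(pass) = 0.531 + 0.354 = 0.886; product 0.803.
Under 7.f with g = 10%: P(escalate) = 0.531 + 0.199 = 0.730; P(pass) = 0.282 + 0.397 = 0.680; product 0.50.

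| | g = 2% | 5% | 10% | 20% |
|---|---|---|---|---|
| P(escalate), 4.a | 0.91 | 0.91 | 0.91 | 0.91 |
| P(escalate), 4.a with replacement | 0.90 | 0.90 | 0.89 | 0.87 |
| P(escalate), 7.f | 0.88 | 0.82 | 0.73 | 0.54 |
| Different final action at 300 µg, same subjects | 0.03 | 0.08 | 0.18 | 0.37 |
| P(500 µg is MTD), 4.a | 0.80 | 0.80 | 0.80 | 0.80 |
| P(500 µg is MTD), 7.f | 0.74 | 0.65 | 0.50 | 0.25 |

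The fourth row is the first minus the third, because escalation under 7.f always implies escalation under 4.a. With replacement, the gap in P(escalate) is still 0.03, 0.07, 0.16 and 0.33. It therefore comes from not counting the event, not from the replacement rule.

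**Another starting rate.** Take 5% Grade 3 or higher, plus 5%, 10% or 20% of subjects whose only qualifying event is a Grade 2 immune one, so p = 0.10, 0.15 or 0.25 under 7.f. P(escalate) is 0.97 under 4.a and 0.91, 0.81, 0.60 under 7.f. P(500 µg is MTD) is 0.94 against 0.80, 0.63, 0.32.

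**The case against.** The best defence is that a team reading the whole plan would apply 7.f. Section 4.a does not say that only Grade 3 events count. Section 7.f is the only text headed Dose Limiting Criteria, Sections 11 and 12.b both rely on those criteria, and Section 8 leads back to them. On this view the outlier is one sentence in 4.a and one cross-reference in 7.g. That is probably the intent, and the fix adopts it. But 7.g says the DLT is defined in Section 4, where Grade 3 is the sole criterion, and it says so at the point where the tables are applied.

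Section 3 can be cited for the narrower reading, since it says "Dose escalation is meant to test the safety of the preparation in terms of its non-immunological toxicity". This is weak support. Section 4.a counts every Grade 3 event, autoimmune ones included, and the same paragraph of Section 3 goes on to argue for increasing and decreasing arms to study immunological effects. The conflict does not depend on it.

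There are safeguards. Affected subjects stop dosing under either reading, the Medical Monitor and investigators meet before each new cohort, and Section 17 has separate rules for drug-attributed SAEs, related Grade 4 toxicities and deaths not related to cancer. These make an unreviewed escalation less likely, but no text tells the meeting which definition to use.

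The probabilities rest on assumed rates. At a 2% Grade 2 immune rate, P(escalate) falls only from 0.91 to 0.88, and the large gaps need rates of 10% to 20%. That limits what can be said about size. The row changes follow from the tables without any rate.

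**Conclusion.** The concern holds, and the text must be corrected before dose decisions rest on it. The plan contains two DLT definitions without an order of precedence, and following each as written can give different dose actions and a different MTD from the same events. That conclusion needs no assumption about rates. How often it would happen is uncertain: a different final action for the 300 µg cohort in roughly 3% to 37% of trials, if 10% of subjects have Grade 3 or higher events, 2% to 20% independently have Grade 2 immune events, and removed subjects are not replaced.

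**What to change.** Make Section 7.f the single DLT definition.

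- **4.a:** define a DLT as any event meeting the criteria in 7.f, and list all three: Grade 3 or higher toxicity, Grade 2 or higher autoimmune toxicity other than vitiligo, and Grade 2 or higher hypersensitivity.
- **7.g:** refer to 7.f for the DLT and to Section 4 for the immune-response endpoints only.
- **11:** replace the reference to Section 8 with 7.f.
- **12.b:** name 7.f in place of the unspecific back-reference.
- **7.g and 12.a:** add that a subject removed under 7.f counts as a DLT, is evaluable for the MTD and is not replaced.

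This is a wording amendment that needs no new data or visits. Its cost is a DLT count that may look less favourable, and a higher chance of expanding to six or de-escalating.
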